6.7.2. Dose Decreases of Parsaclisib/Placebo for Toxicity

Parsaclisib or matching placebo should be interrupted/decreased first, with no change to the ruxolitinib dosage. Adjustments to ruxolitinib may be utilized if interruption/dose adjustment of parsaclisib or matching placebo does not lead to resolution or at least improvement of the AE within a 14-day period (see Section 6.7.7). Treatment with parsaclisib or matching placebo may be delayed up to 2 weeks (14 days) to allow for resolution of toxicity. Participants may resume

treatment if no medical condition or other circumstance exists that, in the opinion of the investigator, would make the participant unsuitable for further participation in the study. The treating investigator should contact the sponsor to discuss the case of any participant whose treatment has been delayed for more than 14 days before restarting treatment with piasclisib or matching placebo and/or ruxolitinib. Adverse events that have a clear alternative explanation or transient (≤ 72 hours) abnormal laboratory values without associated clinically significant signs or symptoms may be exempt from dose-reduction rules.

Table 11 shows dose-reduction and interruption guidelines for piasclisib and matching placebo. Because participants may enter the study with extensive pretreatment and/or severe bone marrow infiltration by the primary disease, these dose-reduction rules are provided as guidelines (see **Table 11**). **Individual decisions regarding dose reduction/interruption should be made using investigator clinical judgment and in consultation with the sponsor's medical monitor in those cases where the guidelines will not be followed, taking into account relatedness of the AE to piasclisib and the participant's underlying condition.** Available dose strengths for piasclisib/matching placebo are shown in **Table 12**.

Table 11: Guidelines for Interruption and Restarting of Piasclisib/Matching Placebo

Adverse Event	Action Taken
Chemistry	

 • AST and/or ALT $> 5.0 \times$ ULN (Grade 3). 	
Step 1: Interrupt piasclisib or matching placebo for up to 2 weeks (14 days) until the toxicity has resolved to \leq Grade 1 except by approval of the medical monitor.
 
Step 2: Restart piasclisib or matching placebo at the same dose. If assessed as related to piasclisib or matching placebo, restart piasclisib or matching placebo at the next lower dose; monitor as clinically indicated.

Hematology	

 • ANC $< 1.0 \times 10^9/L$ (Grade 3) unless because of underlying disease. Applies only if this represents a worsening grade from baseline. • Platelet count $\geq 25 \times 10^9/L$ and $< 40 \times 10^9/L$. Applies only if this represents a worsening grade from baseline. 	
Step 1: Interrupt piasclisib or matching placebo for up to 2 weeks (14 days) until the toxicity has resolved to \leq Grade 1 or pretherapy baseline.
 
Step 2: Restart piasclisib or matching placebo at the same dose and monitor as clinically indicated.

 • Grade 4 ANC ($< 0.5 \times 10^9/L$) regardless of baseline grade. • \geq Grade 3 ANC with temperature of at least $38.5^\circ C$ OR with \geq Grade 3 infection regardless of baseline grade. • Platelet count is $< 25 \times 10^9/L$ (Grade 4), regardless of baseline grade. 	
Step 1: Interrupt piasclisib or matching placebo for up to 2 weeks (14 days) until the toxicity has resolved to \leq Grade 1 or pretherapy baseline.
 
Step 2: Restart piasclisib or matching placebo at the next lower dose; monitor as clinically indicated. Escalate to original dose with recovery to preinterruption levels of analyte.

Nonhematologic toxicities	

 • Diarrhea/colitis (Grade 1) 	
Step 1: Treat with antimotility agents (eg, loperamide) and initiate supportive care. If not improved after 48 hours, treat per guidance for Grade ≥ 2.

Table 11: Guidelines for Interruption and Restarting of Parsaclisib/Matching Placebo (Continued)

Adverse Event	Action Taken

 • Diarrhea/colitis (Grade 2) 	
Step 1: Interrupt parsaclisib or matching placebo. Perform workup for infection (including CMV, Clostridium difficile, etc) immediately. Initiate or continue supportive care. Monitor approximately every 48 hours until resolution.
 
Step 2: If improved within 48 hours and/or infection* is confirmed, restart parsaclisib/matching placebo at the same schedule and dose after resolved to \leq Grade 1 and continue to monitor.
 
*For infectious diarrhea/colitis, follow institutional standard of care guidelines and restart parsaclisib/matching placebo according to clinical judgment after resolved to \leq Grade 1. Consult with medical monitor if needed.
 
Step 3: If not improved within 48 hours and infection is ruled out, start oral steroids or consider IV steroids if participant is being given IV fluids. If no improvement with oral steroids, switch to IV steroids.
 
Step 4: When diarrhea resolves to \leq Grade 1, continue supportive care and taper steroids according to institutional standard of care. When taper is complete (eg, no steroid or \leq 10 mg/day prednisone or equivalent) and diarrhea is \leq Grade 1, restart parsaclisib/matching placebo at the next lower dose with approval of the medical monitor.
 
Step 5: If Grade 2 diarrhea reoccurs, treat per guidance for diarrhea (\geq Grade 3)/noninfectious colitis.
 
Step 6: If \geq Grade 2 diarrhea reoccurs a third time, permanently discontinue parsaclisib/matching placebo.


 • Diarrhea (\geq Grade 3) Noninfectious colitis (any grade; confirmed or suspected) 	
Step 1: Interrupt parsaclisib. Perform workup for infection (including CMV, C difficile, etc) immediately. Initiate or continue supportive care (see Section 6.7.3). Consider colonoscopy with biopsy for diarrhea \geq Grade 3 and/or if symptoms suggestive of colitis (diarrhea accompanied by abdominal pain and/or mucus or blood in stool). Monitor every 48 hours until resolution.
 
Step 2: If infection* is ruled out, start oral steroids or consider IV steroids if participant is being given IV fluids. If no improvement with oral steroids within 48 hours, switch to IV steroids.
 
*For infectious diarrhea/colitis, follow institutional standard of care guidelines and restart parsaclisib according to clinical judgment after resolved to \leq Grade 1. Consult with medical monitor if needed.
 
Step 3: When diarrhea/colitis resolves to \leq Grade 1, continue supportive care and taper steroids according to institutional standard of care. When taper is complete (eg, no steroid or \leq 10 mg/day prednisone or equivalent) and diarrhea/colitis is \leq Grade 1, restart parsaclisib with approval of the medical monitor. Continue to monitor.
 
Step 4: If \geq Grade 3 diarrhea or noninfectious colitis (any grade) reoccurs, permanently discontinue parsaclisib/placebo.

Table 11: Guidelines for Interruption and Restarting of Parsaclisib/Matching Placebo (Continued)

Adverse Event	Action Taken

 • Pneumonitis (Grade 1) 	
Step 1: Interrupt parsaclisib or matching placebo until the toxicity has resolved.
 
Step 2: Restart parsaclisib or matching placebo at the next lower dose. Monitor as clinically indicated.

 • Pneumonitis (\geq Grade 2) 	
Permanently discontinue parsaclisib or matching placebo.

 • Skin toxicity (eg, rash, pruritus, etc, unless otherwise specified) (Grade 2-3) 	
Step 1: Interrupt parsaclisib or matching placebo until the toxicity has resolved to \leq Grade 1.
 
Step 2: Restart parsaclisib or matching placebo at the same dose. If assessed as related to parsaclisib or matching placebo, restart at the next lower dose.


 • Exfoliative dermatitis (Grade 1) 	
Step 1: Interrupt parsaclisib or matching placebo until the toxicity has resolved.
 
Step 2: Restart parsaclisib or matching placebo at the next lower dose. Monitor as clinically indicated.

 • Exfoliative dermatitis (\geq Grade 2) 	
Permanently discontinue parsaclisib or matching placebo.

 • Intestinal perforation (any grade) 	
Permanently discontinue parsaclisib or matching placebo.

 • PJP 	
Interrupt parsaclisib or matching placebo. Permanently discontinue parsaclisib or matching placebo if PJP is confirmed.

 • CMV infection 	
Participants with CMV viremia without associated clinical signs of CMV infection should be carefully monitored. Consider interrupting parsaclisib or matching placebo for participants with CMV viremia and clinical signs of infection until the infection has resolved. Restart parsaclisib or matching placebo reduced by 1 dose level if approved by the medical monitor.

 • Varicella zoster infection 	
Interrupt parsaclisib or matching placebo. Restart parsaclisib or matching placebo only by approval of the medical monitor.

 • Any Grade 1 or Grade 2 toxicity unless otherwise specified. 	
Continue parsaclisib or matching placebo treatment and treat the toxicity; monitor as clinically indicated.

 • Any Grade 3 toxicity, if clinically significant and not manageable by supportive care unless otherwise specified. 	
Step 1: Interrupt parsaclisib or matching placebo for up to 2 weeks (14 days) until toxicity resolves to \leq Grade 1.
 
Step 2: Restart parsaclisib or matching placebo at the same dose. If assessed as related to parsaclisib or matching placebo, restart at the next lower dose. If interrupted for $>$ 14 days, contact the medical monitor for approval to restart parsaclisib or matching placebo. Monitor as clinically indicated.

 • Any recurrent Grade 3 toxicity after 2 dose reductions. 	
Discontinue parsaclisib or matching placebo administration and follow-up per Protocol. Exceptions require approval of sponsor.


 • Any other Grade 4 toxicity. 	
Discontinue parsaclisib or matching placebo administration and follow-up per Protocol. Exceptions require approval of sponsor.

Table 12: Dose Strengths for Parsaclisib/Matching Placebo

Current Dose Level	Dose After 1 Reduction	Dose After 2 Reductions
5 mg QD	2.5 mg QD	1 mg QD
2.5 mg QD	1 mg QD	Contact medical monitor
1 mg QD	Contact medical monitor	Contact medical monitor

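### Protocol Table 11 puts Grade 1 and Grade 2 noninfectious colitis under two rows with different instructions and does not say which row prevails

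*Protocol*

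**What the plan says.** Three consecutive rows of Protocol Table 11 (Section 6.7.2) deal with diarrhea and colitis.

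- **Grade 1 row**, headed "Diarrhea/colitis (Grade 1": the action is "Treat with antimotility agents (eg, loperamide) and initiate supportive care". There is no interruption step and no infection workup. An event not improved after 48 hours moves to the guidance for Grade 2 or higher.
- **Grade 2 diarrhea/colitis row**: Step 1 interrupts study drug and calls for an immediate infection workup. Step 2 covers events that improve within 48 hours and/or prove infectious: after resolution to Grade 1 or lower, "restart parsaclisib/matching placebo at the same schedule and dose". Step 3 starts steroids if there is no improvement within 48 hours and infection has been excluded. Step 4, after the taper, says "restart parsaclisib/matching placebo at the next lower dose with approval of the medical monitor". Step 5 sends a recurrence of Grade 2 diarrhea to the third row. Step 6 applies when "diarrhea reoccurs a third time, permanently discontinue parsaclisib/matching placebo".
- **Third row**, for diarrhea of Grade 3 or higher and for "Noninfectious colitis (any grade; confirmed or suspected": Step 1 interrupts and works up for infection immediately. Step 2 starts steroids once infection is excluded. Step 3, after the taper, says "restart parsaclisib with approval of the medical monitor". Step 4 applies when "diarrhea or noninfectious colitis (any grade) reoccurs, permanently discontinue parsaclisib/placebo".

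The text before the table presents these rules as guidelines. Decisions rest on investigator judgment, with medical monitor consultation where the guidelines will not be followed. Protocol Section 9.5 lists colitis as an adverse event of special interest (AESI) without a grade limit.

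**The concern.** The first two rows sort events by grade, and the third sorts partly by grade and partly by cause. A Grade 1 or 2 colitis that is noninfectious, or only suspected to be, satisfies a heading of each kind. If the instructions agreed, the overlap would be harmless, but they do not.

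The choice of row affects whether the drug is interrupted, when steroids begin, what dose is resumed and possibly when treatment ends for good. Protocol Section 6.7.4 also directs investigators to Table 11 for managing events of possible immunologic origin, so this is the table a site would consult. In the analysis, SAP Sections 9.2.2 and 9.2.3 tabulate AESIs and the events leading to interruption, dose reduction and discontinuation. Those counts would partly reflect which row each site followed.

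**Working it through.** No arithmetic beyond counting episodes applies, and the plan gives no figure to reproduce. The check sets the rows side by side for a noninfectious colitis.

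| Event | By-grade row | Any-grade noninfectious colitis row | Agree? |
|---|---|---|---|
| Grade 1, first action | Antimotility and supportive care; no interruption step | Interrupt; immediate infection workup | No |
| Grade 1, steroids | None in this row; escalates if not improved after 48 hours | Once infection is excluded | No |
| Grade 2, first action | Interrupt; immediate infection workup | Interrupt; immediate infection workup | Yes |
| Grade 2, steroids | Only if not improved within 48 hours and infection excluded | Once infection is excluded | No |
| Grade 2, restart without steroids | Same dose if improved within 48 hours | No such path | No |
| Restart after taper | Next lower dose, with monitor approval | Monitor approval; no dose level given | Incomplete |
| Permanent stop | Third time (Step 6) | First recurrence (Step 4) | Depends on reading |

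**Can the by-grade rows be limited to infectious cases?** No. Step 3 of the Grade 2 row acts only after infection has been excluded, so that row covers noninfectious events. The Grade 1 row has no workup that could separate the causes. The third row applies on suspicion alone, before the cause is known.

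**Does the Grade 1 row mean that the drug continues?** It does not say so. That follows from the absence of an interruption step, together with the table's default row, which continues treatment for Grade 1 or 2 toxicity unless otherwise specified.

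**Permanent stop.** Steps 4 to 6 of the Grade 2 row name only diarrhea. A clash therefore exists only if the row heading, which names colitis as well, extends those steps to colitis. On that reading:

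- Third row: the first recurrence is episode 2.
- Step 6, if it means the third episode: episode 3, a gap of 3 − 2 = 1 episode.
- Step 6, if it means the third recurrence: episode 4, a gap of 4 − 2 = 2 episodes.

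Step 5 does not settle this. It sends a recurrence to the third row. If the earlier Grade 2 episode counts as a first occurrence there, Step 4 of that row stops treatment at once and Step 6 could never be reached for noninfectious colitis. If it does not count, the third row starts again at its Step 1. The text does not say which.

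**The case against.** The strongest defence is that the table works as an escalation pathway. The third row describes symptoms suggestive of colitis (diarrhea with abdominal pain, or with mucus or blood in the stool), so a sensible reader could let the more specific row govern once colitis is suspected. Step 5 links the rows. The rules are guidelines, both restarts after steroids need medical monitor approval, and Section 6.7.4 asks that suspected immune-related events be discussed with the monitor when possible.

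This defence reduces the ambiguity but does not remove it. No precedence rule is written, and the by-grade headings name colitis outright. Consultation is required when the guidelines will not be followed, but here following one row means departing from another, so a site cannot tell when that requirement applies. The guideline status does mean that sites *may* differ. The documents do not support saying that they will.

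A reader might also infer three stronger points that the documents do not support:

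- *Opposite first actions at both grades.* At Grade 2 both rows interrupt and work up immediately. The difference in first action is confined to Grade 1.
- *A restart dose that runs against severity.* The third row states no dose level. That is an omission, and silence does not amount to a higher dose.
- *A bias in the primary endpoint, mainly in the parsaclisib arm.* SAP Section 7.3.1 does count stopping treatment before Week 24 as nonresponse. But it does not say whether stopping parsaclisib/placebo alone counts, the documents give no colitis rate for the combination, and the same table applies to both blinded arms. Section 6.7.4 places most immune-related events after the first 9 weeks, leaving 24 − 9 = 15 weeks for onset, resolution, any taper, restart and recurrence. Section 6.7.6 separately requires a permanent stop for delays beyond 14 days unless the sponsor approves longer.

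**Conclusion.** Table 11 is wrong as written for Grade 1 and Grade 2 noninfectious or suspected noninfectious colitis, because two rows apply and neither is given precedence. The conflict is plainest at Grade 1, where the first action and the steroid trigger both differ. At Grade 2 it is limited to the steroid trigger and the restart path, with the restart dose level missing from the any-grade row. The permanent-stop conflict, a gap of one or two episodes, is conditional on the Grade 2 row's heading extending its recurrence steps to colitis.

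The consequences are possible differences between sites in managing an AESI, and less interpretable interruption, dose reduction and discontinuation tables. The number of participants affected cannot be derived from the documents. Nothing here shows an effect on the primary endpoint.

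**What to change.** The sponsor's clinicians should reconcile the three rows so that each grade and type of diarrhea or colitis has:

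- one action path;
- one stated restart dose level;
- one unambiguous trigger for permanent discontinuation, saying whether episodes or recurrences are counted and whether it covers diarrhea, colitis or both.

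Which clinical rule applies is for them to decide, and none is proposed here. The change is a table correction, issued as a clarification or protocol amendment. It needs no new procedures, data collection or analyses.

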6.7.3. Supportive Care for Diarrhea/Colitis

Participants should be informed to immediately report to the investigator any event of diarrhea. Participants should receive appropriate supportive care measures as deemed necessary by the investigator. For any \geq Grade 1 diarrhea, participants should be advised to drink liberal quantities of clear fluids. If sufficient oral fluid intake is not feasible, fluid and electrolytes should be substituted via IV infusion. Participants should try to eat 5 to 6 small meals per day; low-fat, high-protein foods; and cooked instead of raw vegetables. Participants may supplement their diet with bananas, rice, applesauce, and toast to reduce the number of bowel movements and may also try crackers, gelatin, noodles, or oatmeal. Participants should avoid fried, fatty, greasy, or spicy foods; milk, milk products, and acidic drinks; high-fiber foods and foods that cause gas; and alcohol, caffeine, and herbal supplements (Coutré et al 2015).

For each occurrence, attempts should be made to rule out other causes, such as metastatic disease or bacterial or viral infection (including CMV), which might require additional supportive care.

It may be necessary to perform conditional procedures such as colonoscopy with biopsy as part of evaluation of the event. Note that several courses of steroid tapering may be necessary because symptoms may worsen when the steroid dose is decreased.

Participants should be carefully monitored for signs and symptoms of enterocolitis (such as diarrhea, abdominal pain or cramping, and blood or mucus in stool, with or without fever) and of bowel perforation (such as peritoneal signs and ileus).

6.7.4. Follow-Up for Immune-Related Adverse Events

An AE with a potential immunologic etiology, or an irAE, may be defined as an AE consistent with an immune phenomenon associated with study drug exposure after all other etiologies have been eliminated. Immune-related AEs may be expected based on previous experience with parsaclisib and other drugs (eg, idelalisib) that inhibit PI3K δ . Special attention should be paid to AEs that may be suggestive of potential irAEs. Based on emerging data from the ongoing parsaclisib clinical program (parsaclisib IB), most irAEs occur after the first 9 weeks of study drug administration. However, an irAE could occur at any time. Suspected irAEs should be discussed with the medical monitor when possible.

Participants should receive appropriate supportive care measures as deemed necessary by the treating investigator. Suggested supportive care measures for the management of drug-related AEs with potential immunologic etiology are outlined in Table 11. For each AE, attempts should be made to rule out other causes, including but not limited to metastatic disease or bacterial or viral infection, which might require specific supportive care.

6.7.5. COVID-19

Infection with SARS-CoV-2, the coronavirus that causes COVID-19, is more frequent and severe in patients with hematologic dysfunction ([Jee et al 2022](#)). The presence of hematologic malignancy, baseline neutropenia and lymphopenia, B-cell depletion, and other factors have been identified as risk factors for loss of humoral immunity to COVID-19, poor vaccine response, viral persistence, and severe disease ([Lee et al 2022](#), [Lyudovyyk et al 2022](#), [Shree et al 2022](#)). Targeting B-cell function, proliferation, and survival with various therapies are current strategies for improving the outcome of several hematologic malignancies. PI3K δ inhibition with piasclisib alone or in combination with other therapies, which may also suppress humoral immunity, has the potential to negatively impact SARS-CoV-2 infection risk, vaccine effectiveness, recovery from COVID-19, and disease severity ([Cheson 2022](#)). Investigators and participants in trials of piasclisib, alone or in combination, need to be aware of these potential risks and consider the local standards of care and available therapies for disease prevention, vaccination, and infection management of COVID-19.

6.7.6. Criteria for Permanent Discontinuation of Piasclisib/Matching Placebo

The occurrence of unacceptable toxicity not caused by the underlying disease will be presumed to be related to study drug treatment and will require that the study drug be permanently discontinued. Unacceptable toxicity is defined as follows:

- Occurrence of an AE that is related to treatment with the study drug that, in the judgment of the investigator or the sponsor's medical monitor, compromises the participant's ability to continue study-specific procedures or is considered to not be in the participant's best interest.
- An AE requiring more than 2 dose reductions.
- Persistent AE requiring a delay of therapy for more than 2 weeks (14 days) unless a greater delay has been approved by the sponsor.

See Section [7.1.2](#) for discontinuation procedures.

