Description of change: Specified that individual decisions are in regard to both dose reductions and interruptions.

Rationale for change: To provide additional clarity to dosing decisions.

26. Section 6.7.2, Dose Decreases of Parsaclisib/Placebo for Toxicity (Table 11: Guidelines for Interruption and Restarting of Parsaclisib/Matching Placebo)

Description of change: Removed the requirement for temperature to be measured orally in the event of a Grade 3 or higher ANC and fever, added a description of symptoms of colitis, and added another step for treatment of Grade 3 or higher diarrhea or noninfectious colitis.

Rationale for change: To allow body temperature to be measured by any modality for neutropenic fever and administrative errors.

27. Section 6.7.5, Criteria for Permanent Discontinuation of Parsaclisib/Matching Placebo

Description of change: Removed wording regarding exceptions by sponsor for study drug discontinuation because of AEs requiring more than 2 dose reductions.

Rationale for change: UK MHRA request.

28. Section 6.7.6, Dose Decreases of Ruxolitinib for Safety

Description of change: Clarified that, at the investigator's discretion, ruxolitinib dose interruptions/changes for safety reasons may occur before the end of a 14-day period after the parsaclisib dose was modified or interrupted for safety reasons.

Rationale for change: UK MHRA request.

29. Section 6.8.2, *Pneumocystis jirovecii* Pneumonia Prophylaxis

Description of change: Specified that diaminodiphenylsulfone and pentamidine will not be used for PJP prophylaxis in Japan.

Rationale for change: Japan requirement.

30. Section 6.8.3, Use of Growth Factors Such as Erythropoietin

Description of change: Added section advising caution on concomitant use of growth factors.

Rationale for change: To address multiple questions regarding allowance of growth factors from investigative sites.

31. Section 6.8.4, Restricted Medications and Procedures

Description of change: Modified text regarding use of nonsteroidal anti-inflammatory drugs and added text restricting the dosage of corticosteroids.

Rationale for change: To recommend caution when administering nonsteroidal anti-inflammatory drugs in general and to provide guidance for steroid therapy, which may be used as supportive care, as use of these corticosteroids at high doses may interfere with readout of study endpoints.

32. Section 8, Study Assessments and Procedures

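### Protocol 6.7.6 makes more than 2 dose reductions for an AE a permanent stop without exception, while the overlapping Table 11 row lets the sponsor approve exceptions

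*Protocol*

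**What the plan says.** Protocol Section 6.7.6 states that unacceptable toxicity not caused by the underlying disease "will require that the study drug be permanently discontinued". One of its three definitions of unacceptable toxicity is "An AE requiring more than 2 dose reductions", and that bullet carries no exception. The next bullet, on AEs that delay therapy beyond 14 days, does carry one: "unless a greater delay has been approved by the sponsor".

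Section 6.7.2 contains Tables 11 and 12. The Table 11 row for "Any recurrent Grade 3 toxicity after 2 dose reductions" instructs discontinuation of parsaclisib/placebo and then adds "Exceptions require approval of sponsor". The text introducing the table says that "these dose-reduction rules are provided as guidelines" and leaves room for investigator judgment in consultation with the medical monitor. Table 12 gives the dose ladder from 5 mg QD to 2.5 mg QD to 1 mg QD; the entry for any step beyond that is "Contact medical monitor".

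Section 7.1.1, which lists the reasons for which study treatments must be stopped, includes unacceptable toxicity but refers the reader to 6.7.2.

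SAP Section 7.3.1 counts a participant who stops treatment before Week 24 as a nonresponder on the primary endpoint. SAP Section 7.4.2.2 does the same for the key secondary TSS responder endpoint.

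**The concern.** A rule for permanently stopping the investigational drug should give one answer for one event. Here the section headed as the criteria for permanent discontinuation allows no exception on the number of dose reductions, while the table used in day-to-day dose management allows the sponsor to grant one. The two rules overlap, and nothing in the protocol ranks them.

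What is at stake is first the participant, who could be kept on a drug that another section says must be stopped. Consistent conduct comes second: investigator, medical monitor and sponsor can each cite current text for a different course, and it is unclear whether a continuation approved under Table 11 would be a deviation from 6.7.6. There is also a link to the analysis, because discontinuation before Week 24 fixes a participant's responder status.

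**Working it through.** There is no planned figure to reproduce. The check is a comparison of the current texts, followed by one bound.

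**Step 1: the rules side by side**

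| Place | Trigger | Action | Exception |
|---|---|---|---|
| 6.7.6 | One AE, not caused by the underlying disease, requiring more than 2 reductions | Permanent stop of parsaclisib/placebo | None stated |
| Table 11 row | Grade 3 toxicity recurring after 2 reductions | Discontinue | With sponsor approval |
| Table 12 | Any step below 1 mg QD | Contact the medical monitor | Not addressed |
| 7.1.1 | Unacceptable toxicity | Stop both study treatments | Refers to 6.7.2 |

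**Step 2: where the triggers overlap.** On the Table 12 ladder, 5 to 2.5 mg is reduction 1 and 2.5 to 1 mg is reduction 2. A further reduction for the same AE would be the third, which is more than 2. The general Grade 3 row of Table 11 restarts at the next lower dose when the event is assessed as related. If that AE then recurs at Grade 3 after 2 reductions, the same logic calls for a third. Such an event meets both the Table 11 row and the 6.7.6 criterion.

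**Step 3: what each text allows there.** Table 11 lets the sponsor approve an exception to discontinuation; 6.7.6 does not. The missing exception in 6.7.6 is hard to read as mere brevity, because the neighbouring bullet spells one out.

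**Step 4: the cross-reference.** A reader who starts at 7.1.1 and follows its reference reaches 6.7.2, which holds the text with the exception, and is not sent to 6.7.6, which holds the definition.

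**Step 5: bound on the primary endpoint.** The planned arm size is 440/2 = 220 (Protocol 10.1). If one participant who would have been a responder is instead classed as a nonresponder, that arm's rate moves by 1/220 = 0.45 percentage points. This is an upper bound per participant, because not everyone would have responded. Weighting by the parsaclisib-arm response rates assumed in Protocol 10.1 gives:

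- normal platelet count: 0.582 × 0.4545 = 0.26 points;
- low platelet count: 0.294 × 0.4545 = 0.13 points.

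The weighted values assume that a participant already at the lowest dose responds at the average rate, which the documents do not support or refute. The number of participants who would need a third reduction before Week 24 is not given, so no total can be computed.

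**The case against.** The strongest reply is that the texts can be read together. Stopping the drug and contacting the medical monitor satisfies 6.7.6, Table 11 and Table 12 at once. Table 11's default is also to discontinue, and its exception never compels continued dosing. Section 6.7.6 is headed as criteria and uses mandatory wording, while Table 11 is described as guidelines, so 6.7.6 can be taken as controlling. The triggers also differ. A recurrence caused by the underlying disease falls outside 6.7.6, and an unrelated Grade 3 event restarts at the same dose, so no third reduction is required. In those cases the Table 11 exception can operate without touching 6.7.6.

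Much of this stands, and it rules out several stronger readings that a reader might infer:

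- **That the three places cannot all be followed.** They can, as long as no exception is granted.
- **That Table 12 permits a third reduction.** Its entry directs a contact and grants nothing. It also counts steps from the current dose whatever the cause, whereas 6.7.6 counts reductions required by one AE.
- **That one site would stop while another continues on its own authority.** Exceptions in the Table 11 row need sponsor approval, and that central step limits variation between sites.
- **That the amendment log proves an oversight in Table 11.** For Amendment 1 the log records "Removed wording regarding exceptions by sponsor for study drug discontinuation because of AEs requiring more than 2 dose reductions". That is history; a difference between the log and current text is not an error, and this point does not rely on it.

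The reply does not remove the conflict in the overlap. The ranking of 6.7.6 above Table 11 is inferred and nowhere stated, and 7.1.1 points the other way. An exception approved under Table 11 for an event that also meets 6.7.6 would comply with one passage and breach the other.

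**Conclusion.** The point holds, within limits. The current protocol contradicts itself for one defined case: the same AE, not caused by the underlying disease, recurring at Grade 3 after 2 reductions and needing a third, with a sponsor exception sought. Section 6.7.6 leaves no room for the exception, Table 11 provides for it, and no text says which governs. This is an internal inconsistency in an operative safety stopping rule, and it should be corrected.

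The weight lies on participant safety and consistent conduct. A reader might infer material harm to the primary analysis; the documents do not support that. The effect is at most 0.45 percentage points per affected participant who would otherwise have responded, the event must fall before Week 24, and its frequency is unknown. The bound also assumes that stopping parsaclisib/placebo counts as discontinuing treatment under SAP 7.3.1, which does not specify the drug. Nothing here judges whether exceptions ought to be allowed.

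**What to change.** Reconcile Section 6.7.6, the Table 11 row on recurrent Grade 3 toxicity and the 7.1.1 cross-reference so that they state one rule: whether exceptions to permanent discontinuation exist after 2 reductions and, if so, who approves them. Have 7.1.1 refer to the section that defines unacceptable toxicity. Align the Table 12 entries with the same rule, so that contacting the medical monitor cannot be taken for a separate route. Which rule applies is for the sponsor and its regulators.

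The cost is a change of protocol wording in the next amendment. Sample size, analysis methods and data collection are unaffected.
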